14.2 EARLY STOPPING RULE FOR TOXICITY

In order to confirm the safety of the radiation therapy and cetuximab component of this regimen, patients will continuously be monitored for excessive toxicity and early stopping rules for toxicity will be employed. Unacceptable toxicity is defined as any grade 4 or higher non-hematological toxicity (with the exception of diarrhea, infection, electrolyte abnormalities, nausea and vomiting, hypersensitivity reactions, and neurological dysfunction clearly due to tumor rather than treatment) that does not resolve to less than or equal to grade 2 within 7 days. Stopping rules and the corresponding power calculations are provided in the table below.

# failures/toxicities need to stop the study	Projected probability of failure/toxicity in the populations	Probability of study completion (based on projection)
2 in the first 6 patients 3 in the first 15 patients 4 in the first 26 patients	0.05	.90
5 in the first 50 patients 6 in all 51 patients	0.09	.60
	0.15	0.17

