2.0 OBJECTIVES AND SCIENTIFIC AIMS

Primary objectives:

- 1. To determine the proportion of patients with high-grade astrocytoma and diffuse pontine tumors achieving one year progression free survival.
- 2. To determine the safety of cetuximab administered weekly in conjunction with involved field external beam radiation therapy for diffuse pontine tumors and high-grade astrocytomas.

Secondary objectives:

- 1. To estimate the response rate, time to progression, and overall survival in 2 cohorts of patients (diffuse intrinsic pontine tumors, high-grade astrocytomas) treated on this protocol.
- 2. To explore whether there are any potential associations between primary tumor tissue molecular markers and tumor response.
- 3. To identify CSF protein markers that might indicate the presence of a brain tumor, to validate proteomic methodology by correlating protein and ELISA measurements of known proteins implicated in angiogenesis and tumor progression (VEGF, bFGF, SPARC, attractin), and to explore whether there are any potential associations between histology (grade) with protein and ELISA measurements of those proteins.
- 4. To investigate whether the rash associated with cetuximab is secondary to an inflammatory pathway initiated and mediated by the action of cetuximab on host cells.

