(46/1485) of patients, rarely with fatal outcome (<1 in 1000). Approximately 90% of severe infusion reactions were associated with the first infusion of cetuximab despite the use of prophylactic antihistamines. These reactions were characterized by the rapid onset of airway obstruction (bronchospasm, stridor, hoarseness), urticaria, hypotension, and/or cardiac arrest. Caution must be exercised with every cetuximab infusion, as there were patients who experienced their first severe infusion reaction during later infusions. A 1-hour observation period is recommended following the cetuximab infusion. Longer observation periods may be required in patients who experience infusion reactions.

A 20-mg test dose was administered intravenously over 10 minutes prior to the initial dose to all patients in earlier studies. The test dose did not reliably identify patients at risk for severe allergic reactions.

In the Southeastern region of the United States a higher number of infusion-related anaphylactic reactions to cetuximab have been reported in adult studies than in other areas of the United States [J Clin Oncol 2007, 25:3644-3648 and N Engl J Med 2008, 358:1109-1117].

Pulmonary Toxicity

Interstitial lung disease (ILD) was reported in 3 of 774 (<0.5%) patients with advanced colorectal cancer and in 1 of 796 patients with head and neck cancer receiving cetuximab. Among these four cases, interstitial pneumonitis with non-cardiogenic pulmonary edema resulting in death was reported in one patient with colon cancer. In two of the remaining cases, the patients had pre-existing fibrotic lung disease and experienced an acute exacerbation of their disease while receiving cetuximab in combination with irinotecan. The onset of symptoms occurred between the fourth and eleventh doses of treatment in all reported cases. In the event of acute onset or worsening pulmonary symptoms, cetuximab therapy should be interrupted and a prompt investigation of these symptoms should occur. If ILD is confirmed, cetuximab should be discontinued and the patient should be treated appropriately [Cetuximab package insert. ImClone Systems Incorporated and Bristol-Myers Squibb Company 2006. ER-B0001-03-06].

Dermatologic Toxicity

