12.0 CRITERIA FOR THERAPEUTIC RESPONSE/OUTCOME ASSESSMENT

The study's primary aim is to increase the proportion of patients achieving 1-year progression-free survival. Progression-free is defined as lack of unequivocal tumor progression or treatmentassociated death. Unequivocal tumor progression will be determined (usually via brain MRI) by a POETIC institutional radiologist. If radiological studies suggest possible, but not unequivocal progression, the patient may remain on study until unequivocal progression has been determined. In select cases biopsy may be necessary to distinguish tumor recurrence from radiation effect.

In this study, we will compare the product of 2-dimensional measures of the tumor on the baseline and follow-up MRI scans. Modified Macdonald criteria will be used [J Clin Oncol 1990; 8:1277-1280]. Responses will be defined as:

Complete response: Complete resolution of all tumor.

Partial response: \geq 50% decrease in the 2-dimensional size of the tumor.

Stable disease: < 50% decrease to < 25% increase in the 2-dimensional size of the tumor.

Progressive disease: $(1) \ge 25\%$ increase in the 2-dimensional size of the tumor, or (2) any new tumor focus, or (3) worsening neurological status that cannot be explained by any other cause associated with increase in tumor size (but < 25%).

Determination of favorable responses will be made via comparison to the baseline MRI, while determination of progressive disease will be via comparison to the nadir

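### The toxicity boundary in section 14.2 does not count treatment-related deaths in the exempt classes

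*Combined protocol and SAP*

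**What the plan says.** Primary objective 2 (section 2.0) is "To determine the safety of cetuximab administered weekly in conjunction with involved field external beam radiation therapy" in the two tumor groups. Section 14.2 serves that objective. Its stated purpose begins "In order to confirm the safety of the radiation therapy and cetuximab component of this regimen", and it sets a running boundary over all 51 patients: 2 toxicities in the first 6, 3 in 15, 4 in 26, 5 in 50, and 6 in 51.

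The counted event has three parts:

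- Grade: the definition opens with "any grade 4 or higher non-hematological toxicity (with the exception of diarrhea, infection, electrolyte abnormalities, nausea and vomiting, hypersensitivity reactions". Grade 5 is therefore included, and section 17.2 also uses grade 5 as a category in its reporting table.
- Exceptions, in full: "with the exception of diarrhea, infection, electrolyte abnormalities, nausea and vomiting, hypersensitivity reactions, and neurological dysfunction clearly due to tumor rather than treatment".
- Persistence: the event must be one "that does not resolve to less than or equal to grade 2 within 7 days".

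For one exempt class the documents report fatal cases. Section 11.2 gives severe infusion reactions as approximately 3% ("46/1485) of patients, rarely with fatal outcome (<1 in 1000").

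**The concern.** The exceptions remove whole classes of event and set no upper grade. The closing qualifier about tumor rather than treatment reads naturally with neurological dysfunction only, since it has no sensible meaning for a hypersensitivity reaction. So the opening words bring deaths into the count, and the exceptions take some of them out again.

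Leaving out expected, reversible grade 4 events in these classes is a reasonable choice, because otherwise manageable toxicity could stop the trial. The documents give no reason for leaving out deaths. Section 3.6 states that the combination has not been studied in pediatric patients. The sponsor could therefore report that the boundary was not crossed although a treatment-related death had occurred in an exempt class.

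**Working it through.** **Inputs.** The boundary (2/6, 3/15, 4/26, 5/50, 6/51) is from section 14.2. The sample size is 25 + 26 = 51, from sections 14.1.1 and 14.1.2. The fatal infusion-reaction rate, below 1 in 1000, is from section 11.2. The documents give no exempt-class death rate for this regimen, so every other death rate below is an assumption.

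**Method.** Exact binomial recursion, taking patients as independent with a common rate p. Let f(n, k) be the probability of k events among n patients with no stop so far. Then f(n, k) = f(n−1, k)(1−p) + f(n−1, k−1)p, and any path that reaches the boundary at a look is removed. P(complete) is the sum of f(51, k) over the paths left. Monitoring after every patient or only at the listed looks gives the same result.

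**Step 1: the plan's own figures.**

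| True rate p | Printed P(complete) | Recomputed, boundary as printed | Recomputed, without the 5-in-50 look |
|---|---|---|---|
| 0.05 | 0.90 | 0.862 | 0.906 |
| 0.09 | 0.60 | 0.489 | 0.604 |
| 0.15 | 0.17 | 0.101 | 0.165 |

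The printed boundary does not give the printed probabilities; without the 5-in-50 look it does. That is a separate discrepancy and this point does not depend on it. Results are given both ways where it matters.

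**Step 2: as written.** Let c be the rate of countable toxicity and d the rate of exempt-class death. The boundary sees p = c whatever d is. With c = 0.05, P(complete) is 0.862 (0.906 without the 5-in-50 look) for every value of d.

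**Step 3: if the deaths count.** With the two kinds of event independent, p = 1 − (1 − c)(1 − d).

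- Documented ceiling, d = 0.001: p = 1 − 0.95 × 0.999 = 0.05095. P(complete) = 0.855, against 0.862 as written, a fall of 0.007. Without the 5-in-50 look it is 0.901 against 0.906.
- Stress case, d = 0.05 (expected 51 × 0.05 = 2.55 deaths): p = 1 − 0.95 × 0.95 = 0.0975. P(complete) = 0.419, against 0.862 as written. Without the 5-in-50 look it is 0.536 against 0.906.

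**Step 4: how likely several such deaths are at the documented ceiling.** P(at least one in 51) = 1 − 0.999^51 = 0.050. P(at least two) = 1 − 0.999^51 − 51 × 0.001 × 0.999^50 = 0.0012, about 0.1%.

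**The case against.** The strongest reply is that the numeric boundary is not the only safeguard. A reader might infer that deaths in the exempt classes can never stop the study. The documents do not support that. Section 16.2 provides semi-annual review by the data and safety monitoring committee. Section 16.1 provides a weekly steering-committee call that includes the biostatistical team. Section 17.2 requires notification of serious events within 24 hours and a report for every grade 4 or 5 event, and section 17.2.1 keeps life-threatening infections reportable. Any of these could prompt a stop. What stands is that none carries a numeric criterion or adds to the count in section 14.2.

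The second reply is that the documented risk is low. This is right. The 5% death rate is at least 50 times the only documented fatal rate for an exempt class. A reader might also cite the 3% sepsis figure, or the sudden deaths with radiation plus cetuximab, as deaths the rule would miss. Neither carries over. The sepsis figure comes from colorectal cancer patients on cetuximab with irinotecan or alone. Cardiac arrest and sudden death (4/208) are not exempt classes, and section 11.2 calls their etiology unknown.

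Third, a reader might see a contradiction with the efficacy endpoint, where section 12.0 says "Progression-free is defined as lack of unequivocal tumor progression or treatmentassociated death" and section 14.1 counts any death within one year as progression. It is not a contradiction. The endpoint and the boundary serve different purposes, and the grade wording still works for every class that is not exempt. It does mean that the same death can be a failure in one analysis and carry no weight in the other.

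**Conclusion.** The gap is real and narrow. Under the wording of section 14.2, a treatment-related death from infection, hypersensitivity, diarrhea, electrolyte abnormality, or nausea and vomiting during radiation plus cetuximab does not count toward the only numeric stopping rule for primary objective 2. This follows from the text and needs no assumed rate.

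The size does depend on the rate. At 0.1% deaths on top of 5% countable toxicity, counting them changes completion by less than one percentage point. The stress case shows that the boundary as written cannot react at all if deaths in these classes prove far more common than expected: 0.86 against 0.42, or 0.91 against 0.54 on the version that reproduces the printed table. It is not a forecast. These figures assume independent patients, one rate across both tumor groups, and independence of the two kinds of event.

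This is a cheap improvement to safety monitoring, not an error that undermines the trial.

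**What to change.** Add one sentence to section 14.2: the listed treatment-toxicity exceptions apply to non-fatal events only, and a grade 5 event in those classes attributed to the radiation-plus-cetuximab component counts toward the boundary. Attribution should use the categories already in section 17.2, and the sentence should name which of them count. Neurological dysfunction clearly due to tumor stays excluded. The 7-day resolution clause needs no change, because a death cannot resolve. Patient-level treatment rules are not touched.

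If the sponsor does intend to leave such deaths out, section 14.2 should say so and reconcile this with its grade 4 or higher wording and with primary objective 2.

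The cost is one sentence by amendment and a very slightly higher chance of an early stop when the regimen is safe (0.007 at the documented ceiling, on the printed boundary).

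### Section 14.2: the printed toxicity boundaries give completion probabilities of 0.86, 0.49 and 0.10, not the stated .90, .60 and 0.17, and the 6-in-51 boundary can never be reached

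*Combined protocol and SAP*

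**What the plan says.** Section 2.0 makes safety the second primary objective: "To determine the safety of cetuximab administered weekly in conjunction with involved field external beam radiation therapy". Section 14.2 puts this into practice. It says that "patients will continuously be monitored for excessive toxicity and early stopping rules for toxicity will be employed", and that "Stopping rules and the corresponding power calculations are provided in the table below".

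The first column is headed by the number of "failures/toxicities need to stop the study", so each entry is the count that triggers stopping. The entries are "2 in the first 6 patients 3 in the first 15 patients 4 in the first 26 patients", followed by "5 in the first 50 patients 6 in all 51 patients". The second column, "Projected probability of failure/toxicity in the populations", lists 0.05, 0.09 and 0.15. The third column gives the matching probabilities that the study runs to completion: .90, .60 and 0.17.

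The total of 51 agrees with the accrual targets of 25 (Section 14.1.1) and 26 (Section 14.1.2).

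**The concern.** Two things look wrong on a first reading.

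- The last two boundaries are one patient apart and one event apart. If 5 events by patient 50 already stop the study, it is hard to see how a sixth event at patient 51 could ever be what stops it.
- A boundary of 5 in 50 should stop many trials at a 9% toxicity rate, where 0.09 × 50 = 4.5 events are expected. A 60% chance of completion seems too high.

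The monitoring committee and the IRBs would use this table to judge how the rule behaves. If the probabilities belong to a different rule from the one printed, they have been given operating characteristics that the trial does not have. The rule itself also becomes ambiguous in use: if a fifth toxicity occurs at, say, patient 45, the 5-in-50 row stops the study, whereas the stated probabilities are close to those of a rule that would let it continue.

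**Working it through.** **Inputs (Section 14.2).** Boundaries (n, r): (6, 2), (15, 3), (26, 4), (50, 5), (51, 6). True rates p: 0.05, 0.09, 0.15. Stated completion: .90, .60, 0.17.

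**Method.** Treat patients as independent, each with toxicity probability p, and let X(n) be the cumulative count after n patients. The study completes only if X(6) ≤ 1, X(15) ≤ 2, X(26) ≤ 3, X(50) ≤ 4 and X(51) ≤ 5. Since the count never falls, continuous monitoring and looking only at the listed sample sizes give the same answer. Between looks at n and m patients,

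P(X(m) = k, not stopped) = Σⱼ P(X(n) = j, not stopped) × C(m−n, k−j) p^(k−j) (1−p)^(m−n−k+j),

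keeping only the values of k below the boundary at m.

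**Probability of still running after each look**

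| True rate | after 6 | after 15 | after 26 | after 50 | after 51 | Table states |
|---|---|---|---|---|---|---|
| 0.05 | 0.967 | 0.945 | 0.927 | 0.862 | **0.862** | .90 |
| 0.09 | 0.905 | 0.817 | 0.734 | 0.489 | **0.489** | .60 |
| 0.15 | 0.777 | 0.563 | 0.382 | 0.101 | **0.101** | 0.17 |

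The step from 26 to 50 patients at p = 0.09 can be checked by hand. Trials still running after patient 26 have 0, 1, 2 or 3 events with probabilities 0.0861, 0.2214, 0.2611 and 0.1649. To pass patient 50, the next 24 patients may add at most 4, 3, 2 or 1 events respectively, with probabilities 0.9409, 0.8352, 0.6316 and 0.3508. Then

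0.0861 × 0.9409 + 0.2214 × 0.8352 + 0.2611 × 0.6316 + 0.1649 × 0.3508 = 0.0810 + 0.1849 + 0.1649 + 0.0578 ≈ 0.489.

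Simulation of 200,000 trials per rate gave 0.862, 0.489 and 0.100.

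**Last boundary.** Not stopping at patient 50 means X(50) ≤ 4, so X(51) ≤ 5 < 6. The probability of stopping at 6 in 51 is exactly zero, which is why the last two computed columns are the same.

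**Can another reading recover .90 / .60 / 0.17?**

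| Reading | 0.05 | 0.09 | 0.15 |
|---|---|---|---|
| Stop only when the listed count is exceeded | 0.957 | 0.696 | 0.213 |
| Rule applied within a cohort of 25 | 0.930 | 0.748 | 0.406 |
| Rule applied within a cohort of 26 | 0.927 | 0.734 | 0.382 |
| 5-in-50 row omitted, 6 in 51 kept | 0.906 | 0.604 | 0.165 |
| 5 in 30 in place of 5 in 50 | 0.906 | 0.603 | 0.164 |
| 5 in 38 in place of 5 in 50 | 0.900 | 0.587 | 0.156 |

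No reading that keeps all five printed boundaries matches. The stated figures are approached, to within 2 percentage points, only if the fourth boundary is absent or falls much earlier (about patient 27 to 38), so that 6 in 51 becomes operative.

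**The case against.** The arithmetic is hard to dispute, but its weight can be.

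- **The number 50 may have been misread.** The text was extracted from PDF and the rows of this table are merged. A 30 in place of 50 would nearly restore the stated figures. This cannot be excluded without the source page. However, the entries in this section read cleanly and nothing in it points to a misread digit.
- **A misprint is not proven.** The reconstructions come close but do not match every figure to two decimals (0.906 against .90, 0.165 against 0.17). The stated values might instead have been simulated, rounded or miscalculated. This stands: the documents show that boundaries and probabilities disagree, not which is at fault.
- **The printed rule errs towards caution.** It stops more often than stated at every listed rate, so following it literally does not expose patients to more toxicity than the table implies. The protocol labels none of the three rates as acceptable, and more stopping at 15% may be welcome. The first three boundaries are not in question. All this stands and limits the consequence to a higher chance of early termination.
- **Oversight does not rest on this table alone.** There is semi-annual review by the monitoring committee (Section 16.2), a weekly steering committee call (16.1), 24-hour reporting of serious events (17.2) and removal of patients for intolerable toxicity (13.1). The one-year progression-free tests do not use the table. This is true, but none of it supplies a numerical study-level stopping boundary or resolves the conflict between the rows.

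**Conclusion.** The concern holds. With the boundaries as printed, completion probabilities are 0.86, 0.49 and 0.10, against .90, .60 and 0.17 in the table. These are shortfalls of 3.8, 11.1 and 6.9 percentage points, well beyond rounding. At a 9% toxicity rate the table says the study will more likely than not finish, whereas the printed rule will more likely than not stop it (51.1%). The 6-in-51 row has no effect.

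The ambiguity bears on real decisions. At 9%, the printed rule and the same rule without the 5-in-50 row end differently in 0.604 − 0.489 = 0.115, or about 11.5%, of trials.

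The result assumes independent patients with a common toxicity rate, events counted in order of enrolment, stopping when the listed count is reached, and one rule across all 51 patients. The unreachable last row depends only on how the counts are defined, not on independence or on the rate.

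**What to change.** Check the fourth row against the source document and the original design calculation, then amend the table so that boundaries and probabilities describe one rule.

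- If the printed boundaries are intended, restate completion as 0.86, 0.49 and 0.10 and delete the 6-in-51 row.
- If the fourth row was mis-transcribed, restore the boundary actually used and give the exact probabilities for it.

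Which boundary should apply is for the sponsor and the monitoring committee to decide; the documents do not settle it. The amended text should also say how the probabilities were computed.

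The cost is one table correction by amendment, with no added patients or procedures. Under the first option the stated chance of completing the study becomes less favourable. The correction should be made before the rule is applied, because the conflict affects decisions only from patient 27 onward but would then have to be settled in mid-trial.

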14.3 SECONDARY BIOLOGICAL AIMS

14.3.1 Progression free and overall survival will be calculated using the methods of Kaplan and Meier, separately for the diffuse pontine and high-grade groups. The response rates will be provided along with their 95% confidence intervals for all patients receiving any study medication or radiation.

14.3.2 It is not known how many patients will agree to participate in the components of the study involving (1) correlation of molecular markers and tumor response to therapy, (2) CSF proteomics, and (3) serum inflammatory cytokine levels. These endpoints are exploratory in nature and any analyses will be purely descriptive. Continuous endpoints will be summarized using medians and ranges, categorical data will be tabulated. Changes in measurements will be given in terms of percent change from baseline and change in absolute value.

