1.0 PROTOCOL SUMMARY AND/OR SCHEMA

In this protocol entitled "A phase II trial of external beam radiation therapy and cetuximab followed by irinotecan and cetuximab for children and young adults with newly diagnosed diffuse pontine tumors and high-grade astrocytomas", patients will be enrolled after maximal safe neurosurgical resection (HGA patients) or radiological diagnosis (diffuse pontine tumor patients). They will then receive protocol-prescribed therapy:

- External beam radiation therapy (5940 cGy in 180 cGy fractions) with weekly cetuximab (250 mg/m²/dose).
- 4-8 week rest
- 10 cycles of irinotecan (16 mg/m²/day x 5 consecutive days x 2 weeks) with weekly cetuximab (250 mg/m²/dose) at about 21 day intervals

Research biological evaluations will be performed in consenting patients as an optional portion of the study.

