14.0 BIOSTATISTICS

14.1 DEFINITION OF ENDPOINTS

The primary endpoint of this study is progression free survival at one year. Progression will be measured from initiation of therapy until first documented progression of disease. Death or the unlikely event of loss to follow-up, within one year will also be counted as progression. Those who are alive and progression free one year after initiation of therapy will be considered treatment successes for the evaluation of the primary endpoint.

Response is considered as a secondary endpoint. All patients who have initiated therapy will be evaluated for response. Only patients who were declared ineligible and removed prior to receiving any treatment will be excluded.

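### The HGA response rate is taken over all treated patients, so any patient with no visible tumor after resection dilutes it, and section 12.0 does not name the HGA baseline scan

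*Combined protocol and SAP*

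**What the plan says.** The first secondary objective (section 2.0) is "To estimate the response rate, time to progression, and overall survival in 2 cohorts of patients", so response is reported for the HGA cohort on its own.

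Two places fix the denominator. Section 14.1 states: "All patients who have initiated therapy will be evaluated for response", and excludes only patients found ineligible and removed before any treatment. Section 14.3.1 repeats the all-treated set: "The response rates will be provided along with their 95% confidence intervals for all patients receiving any study medication or radiation". Neither treats absence of tumor at baseline as a reason for exclusion.

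Section 12.0 sets the reference scan: "Determination of favorable responses will be made via comparison to the baseline MRI". It does not say which scan that is for HGA. Section 8.0 requires both a pre-operative and a post-operative MRI for HGA patients and calls neither one baseline. The categories in section 12.0 are changes in a two-dimensional tumor product, with "Complete response: Complete resolution of all tumor" at the top and "any new tumor focus" among the routes to progression. There is no category for a patient who starts with no tumor. Section 12.0 also says "Modified Macdonald criteria will be used".

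Sections 1.0 and 6.1 bring HGA patients in after maximal safe resection or biopsy. Sections 6.1 and 6.2 contain no requirement for residual or measurable tumor, and the radiation guidelines in section 9.1.1 allow for residual disease without assuming it.

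**The concern.** A response rate in a single-arm trial is read as a measure of antitumor activity. If some HGA patients have nothing visible on the scan against which response is judged, they cannot contribute a response whatever the treatment does. The all-treated rate then mixes activity with the proportion of patients whose visible tumor was removed before therapy. Two series with the same activity but different surgical results would report different rates, and the planned output gives no way to separate the two effects.

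The same patients could affect the marker work. Section 10.1 compares expression profiles of responders and non-responders without defining a non-responder. A patient with no visible tumor could be placed among the non-responders because of surgery rather than drug resistance. Section 14.3.2 makes that work exploratory and purely descriptive, so the consequence is limited.

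**Working it through.** **The plan's own figure.** Section 14.1.2 gives n = 26 HGA patients and success at 14 or more progression-free at one year, with a null of 0.35 and an alternative of 0.60. Exact binomial calculation gives type I error 0.0377 and power 0.8007, which agrees with the stated 5% and 80%. This supplies the denominator of 26. The plan states no target, test or precision for response.

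**Inputs**
- N = 26 treated HGA patients (section 14.1.2, assuming all 26 start therapy).
- k = number with no visible tumor on the post-operative MRI. The documents do not give it. Section 3.4 mentions gross total resection, defined there as more than 90%, but gives no proportion and does not equate it with no visible tumor. A range is therefore used.
- r = response rate among the 26 - k patients with tumor. It is not given; 20% and 30% are assumed.
- CI method: section 14.3.1 names none, so exact (Clopper-Pearson) intervals are used.

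**A patient with no visible tumor, taken through section 12.0.** The baseline two-dimensional product is zero.
- Partial response and stable disease are percentage changes from zero, so they are undefined.
- Complete response requires tumor to resolve, and there is none.
- Progression can be reached through a new focus.

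The patient can be scored as progressed but not as responding, and still counts in the denominator under sections 14.1 and 14.3.1.

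**Formula.** With x responders among the 26 - k patients with tumor, the all-treated rate is

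x/26 = [x/(26 - k)] × (26 - k)/26.

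| k | factor (26 - k)/26 | all-treated rate, r = 30% | all-treated rate, r = 20% |
|---|---|---|---|
| 0 | 26/26 = 1.000 | 30.0% | 20.0% |
| 5 | 21/26 = 0.808 | 24.2% | 16.2% |
| 8 | 18/26 = 0.692 | 20.8% | 13.8% |
| 13 | 13/26 = 0.500 | 15.0% | 10.0% |

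**Example in whole patients, k = 8, x = 5**
- Patients with tumor: 5/18 = 27.8%, exact 95% CI 9.7 to 53.5, width 53.5 - 9.7 = 43.8 points.
- All treated: 5/26 = 19.2%, exact 95% CI 6.6 to 39.4, width 39.4 - 6.6 = 32.8 points.
- Check: 27.8% × 0.692 = 19.2%.

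The point estimate falls by 27.8 - 19.2 = 8.6 percentage points. The all-treated interval is narrower only because it counts patients who could not respond.

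**The case against.** The strongest reply is that the denominator rule is explicit and conservative. Every treated patient counts, and anyone who does not meet complete or partial response is a non-responder. That is an ordinary convention for a secondary endpoint with no target or decision rule attached. This stands as a reason to keep the all-treated rate. It does not show that the rate alone answers the first secondary objective for a cohort that enters after resection.

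A second reply is that the missing rule may sit elsewhere. Section 12.0 cites modified Macdonald criteria, and Appendix 2 tabulates the mandated observations. Neither the cited source nor the content of Appendix 2 was available for this review, so a baseline label or an evaluability rule there cannot be excluded. The body text describes Appendix 2 as a summary of evaluations. This point stands and lowers confidence.

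There is also a stronger reading that a reader might infer: that the plan lets surgery move the rate in either direction by a large amount. If all k patients were scored as complete responders because no tumor is seen, the rate would be higher than under non-responder scoring by k/26: 19.2 points at k = 5, 30.8 at k = 8 and 50.0 at k = 13. In the example above, 5/26 would become 13/26 = 50.0% (29.9 to 70.1). A pre-operative baseline would also raise the rate, because resection itself would count as response. The documents do not support giving these readings equal weight. Section 8.0 requires the post-operative MRI specifically for HGA patients and within 30 days before registration, while it exempts the pre-operative scan from that window. The initial radiation volume in section 9.1.1 does use the pre-operative scan, but that is treatment planning, not response assessment. The written complete-response definition presupposes tumor to resolve. The inflating readings are not excluded by the text, but they are strained, and the 50-point figure also needs an assumed k of 13.

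**Conclusion.** The point holds as a dilution problem. On the natural reading, the HGA response rate is multiplied by (26 - k)/26, which is 0.808 at k = 5, 0.692 at k = 8 and 0.500 at k = 13, with no effect at k = 0. This rests on the post-operative MRI being the baseline, on all 26 patients starting therapy, and on a k that the documents do not supply. That the text reviewed does not name the HGA baseline scan is a secondary gap, worth closing because it leaves the strained, inflating readings open.

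The problem concerns patients with no visible tumor, not everyone without measurable tumor. Section 12.0 sets no size threshold for complete response, so a patient whose small or ill-defined residual disappears can meet the written definition.

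The primary one-year PFS tests, both decision rules and the pontine cohort are unaffected. Severity is low to moderate, since only a secondary endpoint and descriptive marker work are touched. Confidence is moderate because of the two sources that could not be checked.

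**What to change.** In section 12.0:
- Name the post-operative, pre-radiation MRI as the response baseline for HGA.
- State that a patient with no visible tumor on it cannot be scored as complete or partial response but is still followed for progression.
- State that a patient with visible but non-measurable residual stays assessable for complete response under the existing definition.

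In section 14.3.1:
- Keep the all-treated rate, saying that patients with no tumor count in it as non-responders.
- Add the HGA response rate with an exact 95% CI among treated patients with tumor present on the baseline scan.
- Report the number with none.
- Use the tumor-present set for the descriptive responder versus non-responder marker comparison in section 10.1.

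Leave the pontine analysis as it is.

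The cost is a short amendment with lead-institution approval and local IRB submission (section 16.0). No new procedure is needed: section 8.0 already requires the scan, and section 16.0 already has baseline imaging recorded. The statistical price is a wider interval for the added rate, 43.8 against 32.8 percentage points in the k = 8 example.
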